#### Part A

##### Period 1

Patients will be screened up to 28 days prior to initiation of study drug. Patients will provide appropriately-obtained informed consent prior to initiating any screening procedures. Patients meeting initial screening criteria will be eligible to continue to the Day 1 (Baseline) visit for review of eligibility and baseline assessments, including SALT assessment, physical examination, clinical laboratory assessments, electrocardiograms (ECGs) and vital signs. Patients meeting all inclusion criteria and none of the exclusion criteria are eligible to enter Part A, Period 1 of the study.

Part A, Period 1 is a double-blind Treatment Period where patients will be randomized to receive either 8 mg BID or 12 mg BID CTP-543 for 24-weeks. Randomization will be stratified by scalp hair loss into one of the following two categories: 1) Partial scalp hair loss (SALT  $\geq 50$  and  $<95$ ); 2) complete or near-complete scalp hair loss (SALT  $\geq 95$ ). Patients will take the first dose of study drug in the clinic on Day 1 and will be instructed to take study drug daily approximately every 12 hours for the duration of Period 1. Other baseline assessments for Part A, Period 1 will include Patient and Clinician Global Impression of disease Severity (CGI-S and PGI-S), and Patient Reported Outcome for Satisfaction (SPRO) and Hair Quality (QPRO). Blood samples for pharmacokinetic assessment will be taken periodically. At End of Treatment (EOT) for Part A, Period 1, treatment success (Responders) will be defined as patients from each dose group having an absolute SALT score of  $\leq 20$  at Week 24. These Responders will enter Part A, Period 2 of the study. Patients having an absolute SALT score  $> 20$  will be defined as a Non-Responder and will have the opportunity to continue receiving treatment in the Open-Label Extension study (CP543.5001) or they will complete treatment at Week 24 and return in 4 weeks for the Post-Treatment Safety Follow-up.

##### Period 2

In Part A, Period 2, patients will be re-randomized to receive either a lower dose of CTP-543 (4 mg BID for patients previously receiving 8 mg BID or 8 mg BID for patients previously

Concert Pharmaceuticals, Inc.  
Statistical Analysis Plan – CP543.2004

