## Part B

Any patient from Part A, Period 2 meeting the LOM criteria (SALT  $> 20$ ) will enter into Part B of the study and return to their original 8 mg BID or 12 mg BID dose assigned in Part A, Period 1. Patients will stay on their assigned dose for 24 weeks regardless of whether they meet the criteria for Restoration of Regrowth (ROR) or not. ROR is defined as the patient's attainment of an absolute SALT score of  $\leq 20$ . Assessment of treatment response using SALT for efficacy will occur monthly during the 24-week period. Patients will have the opportunity to continue receiving treatment in the Open-Label Extension study (CP543.5001) or they will complete treatment at Week 24 and return in 4 weeks for the Post-Treatment Safety Follow-up.

Patient safety will be monitored throughout the trial by the Investigator and supported by regular review by the Medical Monitor. Chemistry and hematology laboratory values will be assessed under fasted conditions bi-weekly for the first month of the treatment period (Part A, Period 1 and Part B), followed by every 4 weeks through the remainder of the study (all Parts). Lipid levels will be assessed every 4 weeks throughout the study. In light of the COVID-19 pandemic, challenges in the conduct of study visits may arise from quarantines, site closures, and/or travel limitations. To ensure the safety of trial participants and to minimize risk to trial integrity, alternative methods for drug dispensation and assessments, including telemedicine visits and clinical laboratory blood draws at a local laboratory or via a Home Health Care agency, may be offered for those trial participants who may no longer have access to the investigational site. Significant cytopenias or other hematologic abnormalities will be managed by severity through dose interruption or discontinuation, and signs and symptoms of infection will be closely monitored and treated promptly. Patients who experience intolerable symptoms during treatment may discontinue treatment at the judgement of the Investigator, but will be followed for safety

Concert Pharmaceuticals, Inc.  
Statistical Analysis Plan – CP543.2004

and efficacy assessments for the remainder of the study unless they withdraw consent. Patients may withdraw consent at any time.

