### **6.3. Prior and Concomitant Medications**

Concomitant medications will be recorded in the eCRF from Screening through the Follow-Up Visit at Week 28, for all Parts/Periods of the study. All medications will be coded using the WHO Drug Dictionary Version 2020-SEP.

Medications are classified as prior if the medication started prior to the first dose date of study drug or as concomitant if used on or after the first dose date of study drug for a given Part/Period.

Prior and concomitant medications will be summarized with counts and percentages separately for the Safety Population by treatment group, WHO Drug ATC classification level 2 and preferred term. For each summary, a patient will be counted only once for each medication.

Prior medications will be summarized for Part A Period 1 only. Concomitant medications will be summarized for each Part/Period.

Partial and completely missing dates will be imputed for the purposes of classifying concomitant medications as follows:

- Partial dates will be imputed following the same algorithm as in Section 9.3 for Treatment-emergent adverse events (TEAEs).
- For an entirely missing start date (i.e. day, month, and year are missing), the start date will be set to the date of administration of study drug for the given Part/Period unless the

Concert Pharmaceuticals, Inc.  
Statistical Analysis Plan – CP543.2004

stop date is prior to the date of administration of study drug, in which case the start date will be set to the stop date.

- For an entirely missing stop date (i.e. day, month, and year are missing), the medication will be treated as ongoing.

Partial dates will be compared to the start and end dates of each Part/Period to determine the study drug administration date that will be used to be imputed.

Prior and concomitant medications will also be listed by-patient.

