### 9.3. Adverse Events

An adverse event is any untoward medical occurrence that may appear or worsen in a patient during the course of a study. It may be a new intercurrent illness, a worsening concomitant illness, an injury, or any concomitant impairment of the patient's health, including laboratory test values, regardless of etiology. Any worsening (ie, any clinically significant adverse change in the frequency or intensity of a pre-existing condition) should be considered an adverse event. A diagnosis or syndrome should be recorded on the adverse event page of the eCRF rather than the individual signs or symptoms of the diagnosis or syndrome. A worsening of the condition under study, alopecia areata, will not be reported as an adverse event.

All patients will be monitored for adverse events during the study. Assessments may include monitoring of the following parameters: the patient's clinical symptoms, laboratory, physical examination findings, or findings from other tests and/or procedures.

Adverse events will be coded using MedDRA version 23.1, and summarized by treatment group, system organ class, and preferred term for each Part/Period of the study.

An adverse event reported after informed consent, but before the first dose of study drug (i.e., Day 1), will be considered a pre-treatment adverse event. TEAEs will be defined as any adverse event that occurs after administration of the first dose of study drug in each Part/Period (ie, on or after the day of the first dose in each Part/Period). Adverse events will further be considered treatment-emergent with respect to a given Part/Period if the adverse event occurred after administration of the first dose of study drug in that Part/Period and, if the patient continues onto a subsequent period part, prior to the first dose of study drug in the subsequent Part/Period. Adverse events will be limited to those collected within this protocol (ie, for rollover patients, AEs collected under the protocol of the rollover study but not in this study will not be in this

Concert Pharmaceuticals, Inc.  
Statistical Analysis Plan – CP543.2004

study). The number and percentage of patients who report TEAEs will be summarized by treatment group, system organ class, and preferred term.

Treatment emergent adverse events will also be summarized by intensity as well as relationship to study drug.

Partial dates will be imputed for the purposes of defining TEAEs as follows:

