Table	14.1.8.1	Summary of Prior Medications	Safety Population	
Table	14.1.8.2.1	Summary of Concomitant Medications — Part A Period 1	Safety Population	Y
Table	14.1.8.2.2	Summary of Concomitant Medications — Part A Period 2	Safety Population	Y
Table	14.1.8.2.3	Summary of Concomitant Medications — Part B	Safety Population	
Table	14.2.1.1	Part A Period 2 Co-Primary Endpoints: Patients with Loss of Regrowth Maintenance (SALT Score $>20$ ) versus Responders (SALT Score $\leq 20$ )	Efficacy Population	Y
Table	14.2.1.2	Part B Primary Endpoint: Patients with Restoration of Regrowth (SALT Score $\leq 20$ ) at Week 24	Efficacy Population	
Table	14.2.2.1	Patients with Absolute SALT Score $\leq 20$ at Weeks 4, 8, 12, 16, 20, and 24 — Part A Period 1	Efficacy Population	Y
Table	14.2.2.2	Patients with Loss of Regrowth Maintenance (SALT Score $>20$ ) or Response (SALT Score $\leq 20$ ) at Weeks 4, 8, 12, 16, 20, and 24 — Part A Period 2	Efficacy Population	Y
Table	14.2.2.3	Patient with Restoration of Regrowth (SALT Score $\leq 20$ ) at Weeks 4, 8, 12, 16, 20, and 24 — Part B	Efficacy Population	

Concert Pharmaceuticals, Inc.  
Statistical Analysis Plan – CP543.2004

Type	Number	Title	Population	For abbreviated report?
Table	14.2.2.4	Mixed Model for Repeated Measures Analysis of Relative Change from Part A Period 1 Baseline in Total SALT Scores by Treatment Group and Visit — Part A Period 1	Efficacy Population	Y
Table	14.2.2.6.1	Mean, Mean Change, and Mean Relative Change from Part A Period 1 Baseline in Total SALT Scores by Visit — Part A Period 1	Efficacy Population	Y
Table	14.2.2.6.2	Mean, Mean Change, and Mean Relative Change from Part A Period 1 Baseline in Total SALT Scores by Visit — Part A Period 2	Efficacy Population	Y
Table	14.2.2.6.3	Mean and Mean Change from Part A Period 2 Baseline in Total SALT Scores by Visit — Part A Period 2	Efficacy Population	Y
Table	14.2.2.6.4	Mean, Mean Change, and Mean Relative Change from Part A Period 1 Baseline in Total SALT Scores by Visit — Part B	Efficacy Population	
Table	14.2.2.6.5	Mean and Mean Change from Part A Period 2 Baseline in Total SALT Scores by Visit — Part B	Efficacy Population	
Table	14.2.2.6.6	Mean, Mean Change, and Mean Relative Change from Part B Baseline in Total SALT Scores by Visit — Part B	Efficacy Population	
Table	14.2.2.7.1	Summary of Missing SALT Scores by Treatment Group and Visit — Part A Period 1	Efficacy Population	Y

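### SAP 6.3 gives the concomitant-medication window no end, so drugs first taken in Period 2 or Part B also fall into earlier periods' tables

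*SAP*

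**What the plan says.** SAP 6.3 treats a medication "as concomitant if used on or after the first dose date of study drug for a given Part/Period". It then states: "Concomitant medications will be summarized for each Part/Period". The summaries use the Safety Population, by treatment group, ATC level 2 and preferred term. The data span the whole study: "Concomitant medications will be recorded in the eCRF from Screening through the Follow-Up Visit at Week 28, for all Parts/Periods of the study".

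Part/Period end dates appear in SAP 6.3 only in the date-imputation rule: "Partial dates will be compared to the start and end dates of each Part/Period to determine the study drug administration date that will be used". That serves incomplete dates. It does not classify a drug whose dates are known.

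SAP 9.3 assigns adverse events to periods differently. An event is treatment-emergent for a Part/Period if it occurs after that period's first dose and, for a patient who goes on, "prior to the first dose of study drug in the subsequent Part/Period".

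Treatment changes at each boundary. In Period 2, "patients will be re-randomized to receive either a lower dose of CTP-543" or placebo. Patients with LOM (SALT above 20 in Period 2) "will enter into Part B of the study and return to their original 8 mg BID or 12 mg BID dose assigned in Part A," meaning its first period. SAP 15.4 lists one concomitant-medication table per period, including 14.1.8.2.2, "Summary of Concomitant Medications — Part A Period 2".

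**The concern.** The rule has a lower bound and no upper bound. A course of a drug started and stopped in Part B is used after the first dose of Period 1, of Period 2 and of Part B, so it qualifies for all three tables. Counting a patient once per medication does not prevent this, because that rule works within each summary.

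Two things follow. First, a drug taken on the restored 8 mg or 12 mg BID dose would be shown in the Period 2 table under the placebo or reduced-dose column. Second, who can contribute such counts depends on outcome: only responders go on from Period 1, and only patients with LOM go on from Period 2.

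There is also a reproducibility point. Tables 14.1.8.2.1 and 14.1.8.2.2 are marked for the abbreviated report, which SAP 8.1.3 places after the last patient completes Part A. The final analyses follow completion of Part B. Under the literal rule, these two tables could change between the reports as Part B medications accrue, although Part A is already complete.

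**Working it through.** No figure in either document rests on this rule, so there is nothing of the plan's own to reproduce. The check applies the rule to example drugs and then asks how many patients could be affected.

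**Classification.** The first-dose days are illustrative and follow the target days in SAP Table 2: Period 1 on day 1, Period 2 on day 169 (Week 24), and Part B on day 253 (Week 36, assuming LOM at Period 2 Week 12).

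- Rule as written: count the drug in a period if its last day of use is on or after that period's first dose day.
- Bounded rule, in the manner of SAP 9.3: the same, and the drug's start day is before the next period's first dose day, where there is a next period.

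| Drug used on days | Rule as written | Bounded rule |
|---|---|---|
| 50–60 | Period 1 | Period 1 |
| 200–210 | Periods 1 and 2 | Period 2 |
| 260–270 | Periods 1 and 2, Part B | Part B |
| −10, ongoing throughout | Periods 1 and 2, Part B | Periods 1 and 2, Part B |

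The two rules differ only for drugs first taken after a period has ended. Drugs ongoing across periods are counted alike.

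**Patients who could contribute carried-back drugs to the Period 1 table.** SAP 7.2 plans about 170 patients on 8 mg BID and 130 on 12 mg BID, with about 50 responders expected from each group.

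- 8 mg BID: 50/170 = 29.4%
- 12 mg BID: 50/130 = 38.5%
- Both: 100/300 = 33.3%

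These are shares of patients in whom over-counting is possible, not expected over-counts. They differ by 38.5 − 29.4 = 9.1 percentage points between dose groups, so the scope for over-counting is not equal across the two columns.

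**Patients who could contribute to the Period 2 table.** These are the patients with LOM in each arm. About 25 patients per arm are expected. The documents give no expected LOM rate, so the number could lie anywhere from 0 to 25 per arm.

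**Search for a closing rule elsewhere.** Protocol 13.4.1 specifies only the coding dictionary, ATC class and preferred term. SAP 7.1 assigns protocol deviations to a study part by comparing their dates with the three randomization dates, and SAP 4 removes one day where the treatment dates of adjoining periods coincide. Neither provision extends to medications.

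**The case against.** The strongest reply is that within-period use was plainly intended. The rule speaks of a given Part/Period, the summaries are made per Part/Period, SAP 4 defines start and end dates for each, and the medication listings in SAP 15.4 are split into Part A and Part B. A programmer might well add the bound unprompted. This stands as evidence of intent, but a pre-specified rule should not depend on it, and the contrast with SAP 9.3 leaves room for the literal reading.

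The second reply is that little hangs on these tables. They are descriptive, and neither document uses them to explain LOM. Drugs that may affect hair regrowth or immune response are largely prohibited (protocol 10.5). Deviations that may confound interpretation are classed as major and summarized by study part (SAP 7.1), and by-patient medication listings are planned. This stands, with one gap: a short steroid course agreed with the Medical Monitor might not be a deviation.

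A reader might go further and infer that the rule reverses the ordering of drug use between patients with LOM and patients who maintained regrowth. Assume 0.5 new drugs per 24 weeks at a constant rate, so that the chance of at least one is 1 − exp(−0.5 × weeks/24). A patient with LOM at Week 8 has 15.4% over 8 weeks of Period 2, but 48.7% once 24 weeks of Part B are added. A maintained patient has 39.3% over 24 weeks. The documents do not support that inference as a finding:

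- No planned table compares patients with LOM and maintained patients. The Period 2 columns are the four randomized sequences, each of which can mix both.
- The drug rate has no source in the documents.
- The 15.4% against 39.3% contrast itself reflects shorter Period 2 follow-up in the patient with LOM, so it is not a fair baseline.

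**Conclusion.** The point holds as a gap in a stated rule. SAP 6.3 bounds the medication window below and not above. Followed literally, it counts drugs first taken in Period 2 or Part B in earlier periods' tables, under a treatment the patient was no longer taking.

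Its size is small. Only Tables 14.1.8.2.1 and 14.1.8.2.2 can change in this way; the Part B table has no later period in this study. No efficacy, adverse-event or exposure result depends on the rule. On planned numbers, about a third of Period 1 patients are open to carry-back. The Period 2 share equals the LOM rate, which the documents do not predict. The actual over-count depends on how many new drugs patients start later, for which the documents give no figure.

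The conclusion rests on the rule being programmed as written. It does not support a claim that the tables would mislead about the cause of LOM, or that drug use would appear reversed between outcome groups.

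**What to change.** Replace the classification clause in SAP 6.3 with wording such as:

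> Concomitant for a Part/Period if used on or after its first dose date and, if the patient continues to a subsequent Part/Period, started before the first dose date of that subsequent Part/Period; otherwise started on or before the patient's last visit in this study. Medications ongoing across periods are counted in each period in which they are used.

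The last period should close at the patient's last visit, as in protocol 10.5, and not at the Safety Follow-Up Visit, because patients who enter the open-label extension do not have that visit.

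The cost is one clause in the SAP and the matching program condition; no new data are needed. The change corrects which period a drug belongs to. It does not equalize time at risk in Period 2, where patients with LOM leave early, so the table should still not be read as a comparison of rates.

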#### **6.4. Medical History**

Medical history will be coded with the MedDRA terminology Version 23.1 and summarized as counts and percentages for the Safety Population by treatment group, system organ class, and preferred term for Part A Period 1. A patient will be counted only once for each condition. Conditions will be listed, including the verbatim investigator description of the relevant medical condition, the coded terms (system organ class, preferred term), start date, end date, and whether or not the condition is ongoing.

## 7. STUDY OPERATIONS

### 7.1. Protocol Deviations

A protocol deviation is any noncompliance with the clinical trial protocol or International Council for Harmonization of Technical Requirements for Pharmaceuticals for Human Use Good Clinical Practice requirements. The noncompliance may be either on the part of the participant, the investigator, or the study site staff. Protocol deviations will be recorded on the source documents and with an explanation for the deviation. All protocol deviations will also be recorded as specified in the monitoring plan.

Protocol deviations will be identified by site staff, through medical reviews, and by clinical research associates during site monitoring. Protocol deviations are reviewed by the sponsor on an ongoing basis during the study to classify deviations as minor or major. Deviations that may alter or confound interpretation of the study results will be classified as major deviations.

Protocol deviations will be summarized as counts and percentages by treatment group, deviation severity, and category for all randomized patients by study part. Reported deviation occurrence date will be compared to Part A Period 1 randomization date, Part A Period 2 randomization date, and Part B re-randomization date to determine the study part where the deviation will be summarized.

Deviations will also be presented by patient in a data listing for all randomized patients.

### 7.2. Randomization

#### Part A Period 1

Patients will be randomized such that approximately N = 130 for 12 mg BID and N = 170 for 8 mg BID in an attempt to have approximately equal numbers of patients eligible for Part A, Period 2. Randomization will be stratified by scalp hair loss into one of the following two categories: 1) Partial scalp hair loss (SALT  $\geq$  50 and  $<$  95); 2) Complete or near-complete scalp hair loss (SALT  $\geq$  95).

The randomization schedule will be generated prior to study start. Tablets and packaging of 8 mg and 12 mg CTP-543 will be identical in appearance.

#### Part A Period 2

For each dose group, patients identified as Responders in Period 1 will be randomized in a 1:1 ratio to a dose reduction arm or a placebo (drug discontinuation) arm. For the dose reduction arm, patients previously on 12 mg BID in Period 1 will be assigned to 8 mg BID and patients previously on 8 mg BID will be assigned to 4 mg BID. Given the previous experience with the primary endpoint for Period 1, it is expected that approximately 50 patients from each dose group in Period 1 will be Responders. Consequently, it is expected that approximately 25 patients from each dose group will be assigned to dose reduction and 25 patients will be assigned to drug discontinuation in Period 2.

The randomization schedule will be generated at the end of Period 1. Tablets and packaging for 4 mg CTP-543, 8 mg CTP-543 and placebo will be identical in appearance.

Part B

For each dose group, patients identified as having a LOM following either *dose reduction* or *drug discontinuation* in Part A, Period 2 will be assigned back to the original dose they received in Part A, Period 1. Study drug dosing regimen will be blinded by administering 2 x 8 mg tablets or 2 x 12 mg tablets twice-daily for 24 weeks. Tablets and packaging of 8 mg and 12 mg CTP-543 will be identical in appearance.

A by-patient listing of randomized treatment group and randomization number will be presented for each Part/Period.

All study patients, Investigators, and site study staff will be blinded to study drug assignment for the duration of the study.

